Clinicaltrials.gov ID 43421

Title: Rapid Non-Invasive Brain Stimulation for OCD (oTMS)

Update 4/22/21

Published Results: Accelerated neuromodulation therapy for Obsessive-Compulsive Disorder.

Study Protocol (see published results – citation above for further details)

Between 7/2018 and 7/2019, eligible participants were recruited from the community by advertisements and referrals. Eligibility included being age 18 to 80, meeting OCD DSM-5 criteria, with at least moderate symptoms (Yale-Brown Obsessive-Compulsive Scale [Y-BOCS] score ≥ 18), and having failed \geq one prior adequate trial (using APA Guidelines' dose and duration definitions) of first-line OCD treatment (SRI or CBT). The Stanford Institutional Review Board approved the study, and all participants provided written informed consent. Participants who were already taking an SRI remained on a stable dose for ≥ 12 weeks before study entry. Exclusion criteria were: severe depression (Hamilton Depression Rating Scale [HDRS-17] > 20); age of OCD onset > 30 years; comorbid medical or psychiatric conditions making participation unsafe; or taking medications that increase cortical excitability, inhibit brain excitability, or create hazard with TMS. Subjects planning to commence CBT within 8 weeks before enrollment were also excluded. Independent raters administered the Y-BOCS (primary outcome measure) weekly for 4 weeks. Response was defined *a priori* as a $\geq 35\%$ reduction in Y-BOCS score. The primary outcome was change in Y-BOCS score at Day 14.

Before beginning the accelerated cTBSmod protocol, each participant completed a neuroimaging session that included a resting sequence for determining a personalized frontal pole TMS target and task-based fMRI elicited by the Go/No-Go task (Supplementary Material). All scans were acquired using a 3-tesla GE Discovery MR750 scanner with a NOVA Medical 32-channel head coil and a 3x accelerated multi-band (simultaneous multi-slice) imaging sequence with a repetition time of 2 seconds.

The resting state fMRI sequence was acquired to generate each participant's personalized right frontal pole TMS target (Supplementary Material). The right frontal pole subunit showing greatest connectivity across all the ventral striatum subunits was selected as the stimulation target in each participant (target generation methods and commentaries are provided elsewhere).[5, 10]

Participants received 5 consecutive days of accelerated cTBSmod to the right frontal pole. Each cTBSmod session was comprised of 1800 pulses, delivered in a continuous train of 600 bursts. Each burst contained 3 pulses at 30 Hz, repeated at 6 Hz.[1] Ten sessions were applied per day (18,000 pulses/day, hourly) (90,000 total pulses) using a Magventure Magpro X100. Stimulation was delivered at 90% resting motor threshold (depth corrected). Localite Neuronavigation System was used to position the TMS coil over the individualized stimulation target.

Statistical Analysis Plan

Mann-Whitney nonparametric test with Y-BOCS change score as outcome was conducted to determine the group difference (responders vs nonresponders) in magnitude of change in left and right DLPFC activity, elicited during inhibitory control, from before to after treatment with the cTBSmod protocol. The Wilcoxon signed rank test (i.e., paired test) was used to determine within individual differences between left and right side of the DLPFC in cognitive control activation evoked by the No-Go condition of the Go/No-Go task. One participant was removed from the neuroimaging analysis due to excess motion.

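### The SAP's Mann-Whitney sentence misnames its dependent variable, and under either reading the SAP states no test of the primary outcome, Day 14 Y-BOCS change

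*Combined protocol and SAP*

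**What the plan says.** The Statistical Analysis Plan section has three sentences.

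- The first gives a Mann-Whitney test, its outcome and its purpose together: "Y-BOCS change score as outcome was conducted to determine the group difference (responders vs nonresponders) in magnitude of change in left and right DLPFC" activity. The purpose in full is the "group difference (responders vs nonresponders) in magnitude of change in left and right DLPFC activity, elicited during inhibitory control, from before to after treatment".
- The second assigns a Wilcoxon signed rank test to imaging; it "was used to determine within individual differences between left and right side of the DLPFC in cognitive control activation".
- The third is an imaging exclusion: "One participant was removed from the neuroimaging analysis due to excess motion".

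The Study Protocol section defines response as a fall of at least 35%, and then names the primary outcome: "reduction in Y-BOCS score. The primary outcome was change in Y-BOCS score at Day 14". On the schedule it says: "Independent raters administered the Y-BOCS (primary outcome measure) weekly for 4 weeks". The visit at which response is classified is not stated. Day 14 is the natural inference.

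The document carries an update date of 4/22/21. It cites the published results and sends the reader to them for further detail on the protocol.

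**The concern.** Two things are wrong.

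First, the Mann-Whitney sentence names a clinical score as the outcome and a brain-activity measure as the quantity compared. If the stated outcome was really ranked, a small p-value would largely repeat the definition of response and carry no information about the DLPFC. If DLPFC change was ranked, the imaging test is not circular, but the plan describes it wrongly.

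Second, the Mann-Whitney sentence is the only place in the SAP where Y-BOCS appears. The trial's primary outcome is a Y-BOCS change, and no sentence says how that change is tested or estimated.

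At stake are what the imaging p-value refers to and whether this document contains any plan for the primary outcome.

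**Working it through.** The SAP gives no sample size, alpha, sidedness or effect size, so there is no planned figure to reproduce. The check is a reading of the text, plus a small amount of arithmetic on the literal reading.

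**Step 1. Which variable is ranked?** A two-group Mann-Whitney test needs one grouping variable and one ranked variable. The grouping is responder status. The sentence offers two candidates for the ranked variable: Y-BOCS change (named as outcome) and DLPFC change (named in the purpose). They cannot both be ranked in one test. Two sides of the DLPFC would also need two tests or a stated combination.

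**Step 2. Which was probably meant?** The purpose clause specifies region, sides, task process and time window, and the two sentences that follow both concern imaging. This points to DLPFC change, with Y-BOCS serving only to form the groups. The wording still says otherwise.

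**Step 3. Literal reading, percent change at the classifying visit.** Every responder has a reduction of at least 35% and every nonresponder less than 35%. The groups therefore separate completely, whatever the imaging shows. With n participants and r responders, the exact two-sided p-value is 2/C(n,r):

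| Split | C(n,r) | Exact two-sided p |
|---|---|---|
| 3 vs 4 | 35 | 2/35 = 0.057 |
| 4 vs 4 | 70 | 2/70 = 0.029 |
| 5 vs 5 | 252 | 2/252 = 0.008 |
| 2 vs 6 | 28 | 2/28 = 0.071 |

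The p-value depends only on group sizes and on the method used, which the SAP does not state. For 4 vs 4, the normal approximation gives 0.021 without continuity correction and 0.030 with it. These splits are examples; the actual split is not given.

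**Step 4. Literal reading, raw points.** The SAP says change score without a percentage, so raw points are the more natural meaning. Entry requires participants "with at least moderate symptoms (Yale-Brown Obsessive-Compulsive Scale [Y-BOCS] score ≥ 18"). A participant starting at 18 who falls 7 points has 7/18 = 38.9% and is a responder. One starting at 30 who falls 10 points has 10/30 = 33.3% and is not, although the raw fall is larger. Separation is therefore strong but not total. It weakens further if the change score and the classification come from different visits.

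**Step 5. Does either reading test the primary outcome?** The primary question is whether Y-BOCS changed from baseline to Day 14.

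- DLPFC ranked: Y-BOCS is not tested at all.
- Y-BOCS ranked: the test compares two subgroups with each other and not Day 14 with baseline. Suppose four participants fall by 35% and four rise by 35%. The mean percent change is (4 × 35 − 4 × 35)/8 = 0, yet the 4 vs 4 comparison gives p = 0.029. If every participant responded, there would be no second group and no test, however large the improvement.
- Wilcoxon: it is assigned to left against right DLPFC.

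So the primary outcome has no stated test under either reading.

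**The case against.** The best defence is that this is loose drafting. On that view, the phrase about the Y-BOCS outcome merely identifies the clinical measure behind responder status, and the rest of the section makes the imaging intent clear. As an account of intent this is probably right, and it is why the literal reading should not be presented as what was done. It does not rescue the wording, which assigns the role of outcome to the wrong variable.

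A second defence is that the document was updated after publication, is written in the past tense and refers to the paper for further detail, so the primary test may be described there. That stands as a limit on the claim: the gap is in this SAP and is not shown to be in the trial's reporting.

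Three stronger inferences are tempting, and the documents do not support them.

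- A reader might infer that the imaging result is circular. That would require Y-BOCS change to have been ranked, which the context makes unlikely and the text does not establish.
- A reader might infer that the primary outcome was never analysed. The document shows only that its SAP does not say how.
- A reader might infer that the primary outcome loses its test only if DLPFC change was meant, so that the sentence read literally covers it. It does not: comparing responders with nonresponders is not a test of change from baseline.

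**Conclusion.** The point holds and should be fixed. The Mann-Whitney sentence contradicts itself and most likely misnames its dependent variable. Independently of that, the SAP states no analysis of Day 14 Y-BOCS change.

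The contradiction and the gap rest on the text alone. The statement that the literal test is close to circular rests on the 35% definition. Separation is complete for percent change at the classifying visit, strong but incomplete for raw points, and weaker across different visits. Complete separation does not guarantee p below 0.05, as the 3 vs 4 and 2 vs 6 splits show. The documents give no sample size, mean or SD, so simulated rejection rates would reflect assumed inputs and none are offered as an estimate for this trial. The Wilcoxon comparison of the two sides is unaffected.

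**What to change.** 1. Check the analysis record to see which variable was ranked. If it was Y-BOCS change, rerun the test on the existing data with DLPFC change and label the rerun post hoc.
2. Correct the sentence. The dependent variable is each participant's pre-to-post change in DLPFC activity during inhibitory control. Treat left and right as two tests with a multiplicity statement, or state how they are combined. Say that Y-BOCS is used only to classify response, and at which visit. State sidedness and whether the p-value is exact or approximate.
3. Whatever the answer to items 1 and 2, state the within-participant analysis of Y-BOCS change from baseline to Day 14, with an estimate and confidence interval. Label it pre-specified or post hoc, since the document postdates the publication.

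The cost is a look at the analysis record and a few sentences. No new data are needed. A rerun of the imaging test is needed only if Y-BOCS change turns out to have been ranked.

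### The SAP's Mann-Whitney sentence names as its outcome the Y-BOCS change that also defines the two groups; correct the compared variable and, optionally, add a supplementary Spearman estimate

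*Combined protocol and SAP*

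**What the plan says.** Three statements bear on this point.

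- **Statistical Analysis Plan, first sentence.** The test and its outcome are given as "Mann-Whitney nonparametric test with Y-BOCS change score as outcome was conducted". The same sentence says the purpose is "to determine the group difference (responders vs nonresponders) in magnitude of change in left and right DLPFC activity".
- **Study Protocol, responder definition.** "Response was defined *a priori* as a $\geq 35\%$ reduction in Y-BOCS score". The visit at which response is judged is not stated. The primary outcome is change in Y-BOCS at Day 14, and ratings were weekly for 4 weeks.
- **Statistical Analysis Plan, second test.** "The Wilcoxon signed rank test (i.e., paired test) was used to determine within individual differences between left and right side of the DLPFC". No clinical outcome enters this test.

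The Mann-Whitney comparison is therefore the only analysis described here that links DLPFC change to clinical outcome. The Study Protocol heading also sends the reader elsewhere: "see published results – citation above for further details".

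**The concern.** A two-group rank test needs one grouping and one compared variable. The sentence supplies two candidates for the compared variable. Its opening names Y-BOCS change; its stated purpose names DLPFC change. If Y-BOCS change is the compared variable, it is compared between groups that were made from it, and the result says nothing about the brain measure. A reader of the posted plan cannot tell with certainty which variable was tested.

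A smaller matter follows once the sentence is read as probably meant. The comparison then uses only which side of 35% each participant fell on. If DLPFC change tracks symptom change by degrees, part of that information is dropped, and no continuous estimate is described beside the split.

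**Working it through.** The plan states no sample size, responder count or effect size, so there is no figure of its own to reproduce. Inputs from the document are the 35% rule and the entry score of 18. Every N, group size, correlation and shift below is an assumption.

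**1. Literal reading, percent change as outcome.** Every responder has a larger percent reduction than every nonresponder, so the ranks separate completely. The exact two-sided p-value is 2/C(N,k), with k responders among N:

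- 4 vs 4: 2/70 = 0.029
- 3 vs 7: 2/120 = 0.017
- 5 vs 5: 2/252 = 0.008
- 2 vs 6: 2/28 = 0.071
- 3 vs 4: 2/35 = 0.057
- 3 vs 3: 2/20 = 0.10

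The p-value depends on group sizes alone. It is below 0.05 for many splits, but for none at N of 7 or fewer.

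**2. Literal reading, absolute change as outcome.** The 35% rule needs 0.35 × 18 = 6.3, so 7 points, at the entry score. At an assumed baseline of 36 it needs 0.35 × 36 = 12.6, so 13 points. A nonresponder who falls 12 points from 36 (33%) therefore outranks a responder who falls 7 points from 18 (39%), and separation need not be complete. I took baselines of 18–36, mean reductions of 25, 35 or 45%, an SD of 15 or 25 percentage points, and groups of at least 3 and about 30% of N. In simulation p ≤ 0.05 occurred in 56–79% of runs at N = 8, 72–90% at N = 10, 88–98% at N = 12 and about 99% at N = 20. No DLPFC data were used.

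**3. Intended reading: information kept by the split.** If the relation is graded (bivariate normal), the fraction kept with responder share p is φ(z_p)²/[p(1 − p)]:

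- 30% responders: 0.3477²/0.21 = 0.58
- 50% responders: 0.3989²/0.25 = 0.64

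**4. The effect shape decides which analysis does better.** Simulated power at two-sided 0.05, exact Mann-Whitney against Spearman:

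| Assumed truth | Assumed groups | Mann-Whitney | Spearman |
|---|---|---|---|
| Graded, correlation 0.7 | 4 vs 4 | 19% | 41% |
| Graded, correlation 0.7 | 5 vs 5 | about 30% | 56% |
| Graded, correlation 0.7 | 10 vs 10 | 73% | 92% |
| Step of 2 SD at the cut | N = 10 | 60–68% | 33–58% |
| Step of 1 SD at the cut | N = 10 | 18–21% | 14–21% |

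Part of the small-N gap in the graded rows is the exact test's conservative size. At 4 vs 4 its attainable level is 2/70 = 2.9%, and at 5 vs 5 it is 8/252 = 3.2%. Spearman's simulated level is 4.4% at N = 8 and 4.9% at N = 10.

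**5. Precision of a supplementary Spearman estimate.** The interval is tanh of atanh(r) ± 1.96 × √[(1 + r²/2)/(N − 3)]. For an observed 0.7, atanh(r) = 0.867 and 1 + r²/2 = 1.245:

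- N = 8: −0.11 to 0.95
- N = 10: half-width 1.96 × √(1.245/7) = 0.827 on the z scale, giving 0.04 to 0.93
- N = 20: 0.32 to 0.88

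**The case against.** The strongest reply is that the second half of the sentence already names both the groups and the compared variable, so the words about outcome are a slip. The fuller account sits in the publication, to which the document refers. That reply largely stands as to what was done, and four stronger readings that a reader might infer are not supported.

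- **That a circular test was run.** The document does not show this. The wording fits a mislabelled outcome at least as well, and the publication and Supplementary Material were not available for this review. For the same reason, the absence here of N, group sizes and scan day is not counted as a defect.
- **That the literal test would be significant whatever the DLPFC did.** It would not always be: 2 vs 6 gives 0.071, 3 vs 4 gives 0.057, and absolute change does not reject in every run.
- **That the responder contrast was itself prespecified.** Only the response definition is stated as a priori. The analysis is described in the past tense, in a document that cites the published results.
- **That the split is an error and should give way to a correlation.** Comparing responders with nonresponders is a legitimate question, and under a step at the cut the split generally has more power.

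It is also fair to say that test power is a poor argument for an analysis reported only as an estimate. The case for adding it rests on using the graded information. Its precision at small N is poor.

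What remains is that the plan's only described link between imaging and outcome contradicts itself about which variable was tested.

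**Conclusion.** The point holds as an inconsistency in the text: the named outcome is the measure that forms the groups, and it does not match the stated aim. This conclusion needs no assumption. The consequences under the literal reading depend on unstated group sizes and on whether change is percent or absolute.

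Under the likely intended reading, the split keeps roughly 58–64% of the information if the relation is graded and 30–50% of participants respond. The document does not say whether the relation is graded, so a loss is possible but not demonstrated. The power figures rest wholly on assumed N and effect. The added estimate is therefore an optional improvement to an imaging analysis already reported.

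**What to change.** 1. **Correct the sentence.** State that the compared variable is change in DLPFC activity, left and right, and that the grouping is responder status at a named visit. If the Y-BOCS change score was used in some other way, say how.
2. **Keep the responder contrast and add a continuous estimate beside it.** Label it post hoc and supplementary. Report the Spearman correlation of left and of right DLPFC change with percent Y-BOCS change, each with a 95% interval and a scatterplot, and no added p-values. Percent change matches the scale of the 35% rule. Use the same visit as for response (Day 14 if that was the visit), so that the two analyses share one outcome.

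The cost is one sentence and one descriptive analysis on data already collected. There are three downsides. The interval will be wide at small N. The analysis is post hoc. It asks about monotone association, not a difference between clinical groups.

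Intervals can also be read as tests. With independent sides, the simulated chance of at least one false positive at 0.05 is 5–10% for the two Mann-Whitney tests and 11–15% if two Spearman p-values are added. That is why the addition should stay an estimate.

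### Does the left-right DLPFC comparison have to become a test of treatment change, with adjustment for multiple imaging tests?

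*Combined protocol and SAP*

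**What the plan says.** All of the imaging inference is in two sentences under Statistical Analysis Plan.

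- The first is a Mann-Whitney comparison of responders and nonresponders on "magnitude of change in left and right DLPFC activity, elicited during inhibitory control, from before to after treatment with the cTBSmod protocol". It does not say whether left and right give two tests or are combined into one.
- The second is a paired test: "The Wilcoxon signed rank test (i.e., paired test) was used" for "within individual differences between left and right side of the DLPFC in cognitive control activation evoked by the No-Go condition of the Go/No-Go task". It names no scan and does not say whether the paired values are levels or changes.

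The Study Protocol section gives the context. On stimulation: "Participants received 5 consecutive days of accelerated cTBSmod to the right frontal pole". On the endpoint: "The primary outcome was change in Y-BOCS score at Day 14". The document gives no significance level, multiplicity rule, sample size or responder count. It writes no contrast of left change against right change and no hypothesis that treatment acts more on one hemisphere. It describes no control arm.

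**The concern.** Three features together look like a design fault.

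1. Stimulation is on one side and both hemispheres are analysed, so laterality is an obvious question. Yet the only direct left-right comparison appears to be on activation level. An asymmetry that existed before treatment would make that test significant even if treatment did nothing.
2. If left and right change are tested separately, one significant and one non-significant result invites the conclusion that the sides differ. Those two tests do not test that.
3. Two or three tests are run with no stated adjustment.

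The two sentences also label the signal differently: inhibitory control in one, the No-Go condition in the other. At stake would be an unsupported claim that treatment acts on one hemisphere, and a chance of some false-positive imaging result above the nominal level.

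**Working it through.** The plan has no figure to reproduce. Two-sided alpha of 0.05 per test, the group sizes, and all asymmetry and noise values below are assumptions.

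**Level versus change.** Give each participant a stable left-minus-right asymmetry drawn from a normal distribution with mean d and SD 1. Add independent scan noise (SD 0.7) before and after treatment, and no treatment effect. Apply the signed-rank test to the post-treatment left-minus-right value (level) and to its post-minus-pre difference (change). Rejection rates over 4,000 runs:

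| n | Level, d = 0.5 | Level, d = 1.0 | Change, either d |
|---|---|---|---|
| 6 | 9% | 26% | 3% |
| 10 | 21% | 62% | 5% |
| 15 | 28% | 81% | 5% |
| 20 | 39% | 93% | 5% |

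With noise SD 0.5 and d = 1.0 (3,000 runs), the level test rejects in 31%, 70% and 96% at n = 6, 10 and 20. The pattern is real, but its size depends heavily on d, which the document does not give. Left truly differs from right in every one of these scenarios, so the level test's rejections are correct for the question stated in the plan. They become errors only if read as a treatment effect.

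**One side significant, the other not.** Suppose both sides change equally and each test has 50% power. With correlation r between the test statistics, and ignoring the opposite tail, P(both significant) = 1/4 + arcsin(r)/(2π), and P(exactly one) = 2 × (0.5 − P(both)).

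- r = 0: 2 × (0.5 − 0.25) = 0.50.
- r = 0.7: P(both) = 0.373, so 2 × (0.5 − 0.373) = 0.25.

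This pattern is therefore common without any side difference. It matters only if the sides are tested separately and the contrast is then over-read; the document states neither.

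**Familywise error.** For continuous test statistics:

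- Two independent tests: 1 − 0.95² = 0.0975. Three: 1 − 0.95³ = 0.143.
- Two correlated tests: 0.091 at r = 0.5, 0.083 at 0.7, 0.070 at 0.9, 0.050 at 1.

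Rank tests in small groups are discrete. The smallest exact two-sided Mann-Whitney p-value is 2 divided by the number of possible group allocations:

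| Split | Smallest p | Actual size at 0.05 | Two independent tests |
|---|---|---|---|
| 3 v 3 | 2/20 = 0.100 | 0 | 0 |
| 3 v 4 | 2/35 = 0.057 | 0 | 0 |
| 4 v 4 | 2/70 = 0.0286 | 0.0286 | 1 − (1 − 0.0286)² = 0.056 |
| 5 v 5 | 2/252 = 0.0079 | 0.0317 | 0.062 |
| 3 v 6 | 2/84 = 0.0238 | 0.0476 | 0.093 |
| 6 v 6 | 2/924 = 0.0022 | 0.0411 | 0.081 |

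At a total of 6 or 7 no split reaches 0.05. Adding the exact signed-rank test then gives at most 2 × 0.5⁶ = 3.1% (n = 6) or 6/128 = 4.7% (n = 7). Whether the overall rate exceeds 5% therefore depends on group sizes the document does not report.

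**Cost of Holm.** With two tests the smaller p-value must be at most 0.025. At 4 v 4 the minimum is 0.0286, and at 3 v 5 it is 2/56 = 0.0357. In both cases no data could give a significant result.

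**The case for a change.** The strongest case for a change starts from the contrast between adjacent sentences. One spells out change from before to after treatment and the next omits it, so level is the natural reading. The Study Protocol section describes only the scan before treatment, so the paired test might even use baseline data. If change was intended, the text should say so. Defining the paired value as left change minus right change would need only rewording and a rerun on existing data, and the simulations show it resists a stable asymmetry.

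Much of this stands. Level is the likelier reading, no side-by-time or side-by-response contrast is written, familywise error is not controlled, and a lateralised treatment effect could not be inferred from these tests.

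What does not stand is the step to a required change. The text neither excludes change values nor says that the sides were tested separately. The stimulated site is the frontal pole, not the DLPFC, so a right-sided target does not by itself imply a left-right DLPFC hypothesis. A change-difference test would answer a question the plan does not pose, and with no control arm described it would still not attribute a side difference to treatment. The two labels for the signal need not conflict: No-Go is the inhibition condition of the same task, and task detail is deferred to Supplementary Material. The analyses are also reported in the past tense alongside a published result, so any added contrast would be post hoc.

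**Conclusion.** The concern identifies a limit on interpretation, not an error in the plan. The paired test is suited to its stated purpose, which is to compare left and right No-Go activation within participants. The unstated scan, quantity and number of tests are missing detail that an analyst with the imaging data can supply. Whether to adjust is a fair trade-off for tests outside the primary endpoint: under the assumed 0.05 per test, the two-test familywise error runs from 0 (3 v 3, 3 v 4) to 9.75% (independent continuous tests), while Holm removes any chance of significance at 4 v 4 or 3 v 5. The 26% to 96% rejection rates at a 1 SD asymmetry are not false-positive rates for the plan's own question.

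No change is needed. The imaging p-values are best read as exploratory, and neither a left-right difference in activation nor significance on one side only should be taken as a lateralised treatment effect. This conclusion rests on the absence of any stated lateralised hypothesis; if the investigators made that claim, the left-minus-right change contrast would be needed to support it.
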